5.7.1.3.	Work Productivity and Activity Impairment Questionnaire	30
5.7.2.	Subgroup analyses	32
5.8.	Interim Analyses	33
6.	Supporting Documentation	34
6.1.	Appendix 1 List of Abbreviations	35
6.2.	Appendix 2: Changes to Protocol-Planned Analyses	36
6.3.	Appendix 3: Supporting Study Information	37
6.3.1.	Demographics	37
6.3.2.	Baseline and Disease Characteristics.....	37
6.3.3.	Protocol Deviations.....	37
6.3.4.	Medical and Ophthalmic History.....	37
6.3.5.	Prior/Concomitant/Follow-up medications (including dictionary).....	38
6.4.	Appendix 4: PRO Analysis Instructions.....	39
6.4.1.	Glaucoma Symptom and Health Problem Checklist (SHPC-18) Scoring recommendations:.....	39
6.4.2.	Work Productivity and Activity Impairment Questionnaire Scoring.....	39
6.5.	Data handling convention	39
6.5.1.	Analysis Window.....	39
6.5.2.	Missing Date Imputation.....	40
6.5.2.1.	Missing/Incomplete AE and Medication Start Date.....	40
6.5.2.2.	Missing/Incomplete AE and Medication End Date.....	41
7.	References.....	43

List of Tables

No table of figures entries found.

CONFIDENTIAL

Statistical Analysis Plan V2.0

XEN-45 Gel Stent GPS

SAP Version History

SAP Version History Summary			
SAP Version	Approval Date	Change	Rationale
1.0	01Apr2021	Not Applicable	Original version
2.0	13May2021	Enrolled and ITT populations descriptions updated	updated the SAP for the definitions of ITT and Enrolled Population due to the extraneous data that was included specific to the enrolled by terminated before treatment patients.

CONFIDENTIAL

Statistical Analysis Plan V2.0

XEN-45 Gel Stent GPS

1. Introduction

This statistical analysis plan (SAP) provides a more technical and detailed elaboration of the statistical analyses of the efficacy, safety and patient reported outcome data as outlined and/or specified in the final protocol of Study CMO-US-EYE-0600 (version dated 21 Mar 2019). Specifications of tables, figures, and data listings are contained in a separate document.

This is a multi-center, randomized, parallel group, prospective, open-label clinical trial to evaluate the ability of XEN-45 Gel Stent (XEN) to reduce intraocular pressure (IOP) and reduce the amount of topical IOP-lowering medications in subjects poorly controlled on topical therapy.

Participants will be randomized in 2:1 ratio, resulting in approximately 68 eyes being implanted with XEN and approximately 34 eyes receiving trabeculectomy. Participants will be screened for enrollment, and eligible candidates will be approached to ascertain interest in study participation. Study duration will be approximately 12 months, and Table 1-1 shows the schedule of assessment.

If both eyes meet the inclusion criteria, the investigator will determine the study eye. And only the study eye will be treated with the randomized treatment.

CONFIDENTIAL
XEN-45 Gel Stent

Table 1-1 Schedule of assessment

Procedure / Data to be Recorded	Baseline Qualifying Visit ^a	Preoperative Visit 1 ^a	Operative		Postoperative Visits (visit window; time since Day 0)															
			Visit 2 Day 0	Visit 3 Day 1 (6-48 h)	Visit 4 Week 1 (3-10 d)	Visit 5 Week 2 (11-20 d)	Visit 6 Month 1 (3-8 wk)	Visit 7 Month 3 (9-17 wk)	Visit 8 Month 6 (18-32 wk)	Visit 9 Month 9 (33-47 wk)	Visit 10 Month 12 (48-60 wk)									
Demographics	X																			
Medical and Ophthalmic History	X																			
Subject Eligibility	X																			
Informed Consent/HIPAA	X																			
Concomitant Medications and/or Procedures Review	X	X	X	X	X	X	X	X	X	X	X	X	X	X	X	X	X	X	X	X
Intraocular Pressure (IOP)	X ^b	X	X	X	X	X	X	X	X	X	X	X	X	X	X	X	X	X	X	X
Autorefractor		X							X			X			X					X
Visual Acuity (BCVA) ^c	X	X	X	X	X	X	X	X	X	X	X	X	X	X	X	X	X	X	X	X
Manifest Refraction	X																			X
Biomicroscopy (slit lamp exam)	X	X	X	X	X	X	X	X	X	X	X	X	X	X	X	X	X	X	X	X
Gonioscopy Assessment (Schaffer's Scale) ^d	X				X ^d															X ^d
Visual Field Exam	X ^e														X					X
Ophthalmoscopy		X	X	X	X	X	X	X	X	X	X	X	X	X	X	X	X	X	X	X
Pachymetry		X	X	X	X	X	X	X	X	X	X	X	X	X	X	X	X	X	X	X
Topography ^f		X	X	X	X	X	X	X	X	X	X	X	X	X	X	X	X	X	X	X
Biometry ^f		X	X	X	X	X	X	X	X	X	X	X	X	X	X	X	X	X	X	X
AS-OCT ^f		X	X	X	X	X	X	X	X	X	X	X	X	X	X	X	X	X	X	X
Bleb Photography ^f		X	X	X	X	X	X	X	X	X	X	X	X	X	X	X	X	X	X	X
PRO: SHPC-18 ^g	X		X	X	X	X	X	X	X	X	X	X	X	X	X	X	X	X	X	X
PRO: Postsurgical Question ^g																				
PRO: WPAI ^g	X			X																X
Randomization		X																		
Glaucoma Surgery				X																

CONFIDENTIAL

Statistical Analysis Plan V2.0 |

XEN-45 Gel Stent

	Baseline Qualifying Visit ^a	Preoperative Visit 1 ^a	Operative		Postoperative Visits (visit window; time since Day 0)																
			Visit 2 Day 0	Visit 3 Day 1 (6-48 h)	Visit 4 Week 1 (3-10 d)	Visit 5 Week 2 (11-20 d)	Visit 6 Month 1 (3-8 wk)	Visit 7 Month 3 (9-17 wk)	Visit 8 Month 6 (18-32 wk)	Visit 9 Month 9 (33-47 wk)	Visit 10 Month 12 (48-60 wk)										
Procedure / Data to be Recorded																					
Record Needling and Laser Suture Lysis, and Antibiotic Treatments				X			X		X		X		X		X		X		X		X
Adverse Events Assessment		X		X ^b			X		X		X		X		X		X		X		X

AS-OCT = anterior segment optical coherence tomography; BCVA = Best corrected visual acuity; d = day; h = hour; HIPAA = Health Insurance Portability and Accountability Act; IOP = intraocular pressure; PRO = patient reported outcome; SHPC-18 = Symptom and Health Problem Checklist; wk = week; WPAI = Work Productivity and Activity Impairment

^a The Baseline Qualifying Visit and the Preoperative Visit may be done on the same day if there are no changes in preoperative IOP medications. The Preoperative Visit may be repeated to complete all procedures, if needed. The visit window for Preoperative Visit 1 (including any repeated visits) is up to 4 weeks before study glaucoma surgery in the study eye and ≥ 3 months since previous intraocular surgery in either eye.

^b This is the medicated baseline IOP value. This should be performed at approximately the same time at each visit whenever possible. Subject has taken IOP medication.

^c BCVA should be performed using a Snellen chart with glasses.

^d Performed at Baseline Qualifying Visit and then at other times at the investigator's discretion

^e Can use valid results up to 3 months prior to screening

^f At selected sites only

^g Patient questionnaires should be self-administered prior to any clinical assessments.

^h Refers to intraoperative events or surgical complications

CONFIDENTIAL

Draft Statistical Analysis Plan v2.0

XEN-45 Gel Stent

1.1. Objectives and Endpoints

1.1.1. Objective

To compare the effectiveness and safety of XEN to trabeculectomy in participants with glaucoma refractory to topical medical therapy defined as IOP not at target on 1 or more topical medications.

1.1.2. Primary Endpoint

Percentage of participants achieving $\geq 20\%$ mean IOP reduction from baseline at Month 12 on the same or fewer number of topical IOP-lowering medications, without: clinical hypotony, loss of vision to count fingers, or secondary glaucoma surgical intervention.

1.1.3. Secondary Endpoints

Effectiveness:

- Mean and changes in mean IOP and number of topical IOP-lowering medications from preoperative baseline over time
- Change from baseline (medicated) in mean IOP and mean number of topical IOP-lowering medications at Month 12
- Proportion of eyes achieving specific IOP targets (≤ 18 mm Hg, ≤ 17 mm Hg, ≤ 16 mm Hg, ≤ 15 mm Hg, ≤ 14 mm Hg, ≤ 13 mm Hg, and ≤ 12 mm Hg at Month 12)
- Proportion of eyes achieving specific percentage IOP lower targets from baseline ($\geq 25\%$ to 50% in 5% increments) over time
- Proportion of eyes achieving $\geq 20\%$ IOP reductions and specific IOP targets detailed above on same or lower number of topical IOP-lowering medications at Month 12
- Mean and changes in mean IOP and number of topical IOP-lowering medications from preoperative baseline over time in eyes with medicated baseline IOP ≤ 18 mm Hg
- Needling rates; number of needlings per eye; outcomes post needling, including mean IOP and number of medications measured by proportion of eyes achieving $>20\%$ reduction at Month 12 on same or fewer topical IOP-lowering medications, and number of subjects not using any topical IOP-lowering medications; and antifibrotic use during needling.

Complete and qualified success:

- Complete success (IOP ≤ 18 mm Hg, with 20% or greater IOP lowering from medicated baseline on no topical medications) at Month 12 (eyes with clinical hypotony will be excluded)
- Qualified success (IOP ≤ 18 mm Hg with 20% or greater IOP lowering from medicated baseline with topical medications) at Month 12 (eyes with clinical hypotony will be

CONFIDENTIAL

Draft Statistical Analysis Plan v2.0

XEN-45 Gel Stent

excluded)

- Medication-free eyes, mean IOP in this cohort, and proportion of eyes at specific IOPs (≤ 18 mm Hg, ≤ 17 mm Hg, ≤ 16 mm Hg, ≤ 15 mm Hg, ≤ 14 mm Hg, ≤ 13 mm Hg, and ≤ 12 mm Hg at Month 12)
- Proportion of eyes achieving specific percentage IOP lower targets from baseline ($\geq 25\%$ to 50% in 5% increments) with medication-free eyes.

Intraoperative adjunctive antifibrotic therapy administered:

- Compound/product, mode of administration, dose and concentration, timing of adjunctive agent (surgery day and pre- and postsurgical procedure/implantation).

Visual parameters recovery post surgery:

- Mean and mean change in best corrected visual acuity (BCVA) with current glasses (preoperative and postoperative Day 1; Weeks 1 and 2; and Months 1, 3, 6, 9, and 12)
- Mean and mean change in manifest refraction (baseline and postoperative Months 1, 3, 6, and 12)
- Mean and mean change in surgically induced astigmatism (autorefractor reading [preoperative and postoperative Months 1, 6, and 12] and, at selected sites, topography [preoperative and postoperative Week 1, and Months 1 and 12])
- Mean and mean change in optical biometry (anterior chamber depth and keratometric values) at preoperative and postoperative Day 1 and Week 2 at selected sites.

Other:

- Bleb morphology (anterior segment optical coherence tomography and slit lamp photography at selected sites).

Safety:

- Clinical hypotony defined as vision reduction (2 lines or more) related to macular changes consistent with hypotony maculopathy (macular folds), optic disc edema, and/or serous choroidal detachments because of low IOP
- Eyes with IOP 6 mm Hg or less at any time point and relevant clinical assessment (vision reduction [2 lines or more] related to macular changes consistent with hypotony maculopathy [macular folds], optic disc edema, anterior chamber status, and/or serous choroidal detachments because of low IOP) of these eyes at those time points
- Adverse events (AEs) including specific intraoperative and postoperative events of interest
- BCVA, pachymetry, visual field
- AEs including serious AEs (SAEs)
- Adverse device effects (ADEs) including serious ADEs (SADEs)

CONFIDENTIAL

Draft Statistical Analysis Plan v2.0

XEN-45 Gel Stent

Patient-reported Outcomes:

- Patient-reported Outcomes (PRO)

1.1.4. Exploratory Endpoints

Effectiveness:

- Time to completed success (defined in Section 1.1.3)

Time to qualified success (defined in Section 1.1.3)

1.2. Study Design

This is a post-marketing, multi-center, randomized, parallel group, prospective, open-label clinical trial to evaluate the ability of XEN to reduce IOP and reduce the amount of topical IOP-lowering medications in participants poorly controlled on topical therapy.

Participants will be randomized at a ratio of 2:1, resulting in approximately 68 eyes being implanted with XEN and approximately 34 eyes will receive trabeculectomy. A randomized study design was chosen because it prevents selection bias in treatment assignments and it produces comparable groups. This study will include participants presenting with glaucoma poorly controlled on topical therapy who are candidates for a subconjunctival drainage procedure. Participants will be screened for enrollment and eligible candidates will be approached to ascertain interest in study participation.

Participants can be enrolled into one of the following groups:

Group 1: XEN implanted (XEN group)

Group 2: Trabeculectomy (Trab group)

All inclusion/exclusion criteria, effectiveness endpoints, success rate, and follow up exams will be identical for both groups.

At baseline, participants with glaucoma not at target IOP when using at least 1 topical IOP lowering medication will be screened for eligibility to participate in the study. After the participant is determined to be eligible for participation in the study and is enrolled, the physician may stop the previously prescribed medications 1-4 weeks before surgery and begin preoperative medications (e.g., steroids, antibiotics, artificial tears, oral CAIs) to prepare the ocular surface before surgery. The detection and treatment of comorbid conditions, particularly diseases of the ocular surface disease (dry eye) and blepharitis, can help reduce eye inflammation (Baudouin, 2012). Stopping or reducing IOP lowering medications and replacing them, if necessary, with oral acetazolamide prior to surgery may be considered along with use of topical steroids and preservative-free lubricants to reduce ocular surface inflammation and improve the likelihood of successful implantation (Vera et al, 2018).

CONFIDENTIAL

Draft Statistical Analysis Plan v2.0

XEN-45 Gel Stent

Participants will undergo at least one preoperative visit (and more as needed), and then be scheduled for XEN gel stent implantation or trabeculectomy. Participants will be examined postoperatively at the following intervals: 1 Day, 1 Week, 2 Weeks, 1 Month, 3 Months, 6 Months, 9 Months, and 12 Months.

CONFIDENTIAL

Draft Statistical Analysis Plan v2.0

XEN-45 Gel Stent

2. Statistical Hypotheses

First, let the percentage of participants achieving $\geq 20\%$ mean IOP reduction from baseline at Month 12 on the same or fewer number of topical IOP lowering medications, without clinical hypotony, loss of vision to count fingers, or a secondary glaucoma surgical intervention be denoted by P1 for XEN implanted group and by P2 for trabeculectomy group. By assuming the margin of non-inferiority at 24%, the null hypothesis for this non-inferiority testing is set up as $P1 - P2 \leq -0.24$ vs. the alternative hypothesis as $P1 - P2 > -0.24$.

Equivalently, non-inferiority of XEN to Trab can be declared if the lower limit of the 2-sided confidence interval (CI) of the difference of the above endpoint between the two treatment groups computed using normal approximation is greater than -24%.

CONFIDENTIAL

Draft Statistical Analysis Plan v2.0

XEN-45 Gel Stent

3. Sample Size Determination

The initial sample size calculation in the protocol is provided in the following next two paragraphs.

Recent studies of XEN in treating primary open-angle glaucoma, patients have reported significantly high treatment success rates. Grover et al. reported 75.4% of the treated patients having achieved success, as defined by a > 20% reduction from baseline in IOP at month 12 on the same or fewer medications (Grover, 2017). Mansouri et al. reported 81% success rate at month 12, and Tan et al. (2018) reported success rates of 87% and 92% at month 12 depending on if patients were using medications (Mansouri, 2018; Tan, 2018). However, it should be noted that the three studies are based on relatively small sample sizes in XEN alone arm, ranging from 21 to 61 evaluable study eyes, and a more conservative estimate of the success rate is about 70%. A previous study supported that XEN procedure and the standard of care therapy trabeculectomy are comparable in terms of treatment success (Schlenker, 2017). Moreover, it is assumed that neither treatment is better or worse than the other by more than 20% in terms of treatment success rate. The trial is intended to demonstrate that XEN is comparable to trabeculectomy in terms of treatment success rate. The sample size calculation is based on equivalence test.

To control Type-I error rate at 5% and to attain 80% power for demonstrating that the difference is within the equivalence limit of 18%, about 256 study eyes will be needed for the study with a randomization ratio of 2:1 for the XEN arm: Trabeculectomy arm. Allowing a 10% dropout rate for the first year, approximately 285 study eyes (190 for the XEN arm, and 95 for the trabeculectomy arm) will need to be recruited for the study.

In March 2020, COVID-19 significantly impacted clinical trials globally. The XEN GPS team evaluated the challenging situation facing enrollment of patients in the CMO-EYE-US-0600 XEN GPS study and decided to take a proactive approach to mitigate risk. A note-to-file document was filed on June 2, 2020 to reconsider the study sample size at a lower scale in order not to delay the study completion.

The recalculation still follows the initial sample size calculation by using a non-inferiority approach with an assumed proportion of Trab at 0.70. However, the margin of non-inferiority is changed to 24% from 15%.

SAS PROC POWER with the case of TWOSAMPLEFREQ is employed to yield a total sample size of 102 completors (68 in XEN and 34 in Trab). As a result, the study requires to enroll a minimum of 114 patients (76 in XEN and 38 in Trab) in order to achieve the study goal when 10% dropout rate is taken into account.

CONFIDENTIAL

Draft Statistical Analysis Plan v2.0

XEN-45 Gel Stent

4. Populations for Analysis

The analysis populations will consist of participants as defined below:

- **Enrolled population:** For all study eyes for which subjects have signed ICF and met all inclusion/exclusion criteria.
- **Intent-to-Treat (ITT) population:** all enrolled eyes randomized to study glaucoma surgery (XEN or trabeculectomy), and received study glaucoma surgery (XEN or trabeculectomy).
Note that analyses will be based on the randomized surgery.
- **Safety Population :** All enrolled eyes that have undergone study glaucoma surgery.
Note that analyses will be based on the actual surgery treated.

Due to the nature of Phase 4 study, there will be no mITT population to be implemented, unless there are significant protocol deviations or other reasons.

CONFIDENTIAL

Draft Statistical Analysis Plan v2.0

XEN-45 Gel Stent

5. Statistical Analyses

5.1. General Considerations

- The analysis will be performed after the database is locked and randomization schedule is released.
- All efficacy analyses will be performed using the ITT population. Safety analyses will be performed using the Safety population.
- Efficacy analyses will be performed for the study eye, unless stated otherwise.
- Baseline is defined as the last non-missing value prior to the start of study intervention unless specified in some cases. In general it is preoperative visit (Visit 1). However, there is another medicated baseline for IOP, which is defined at baseline qualifying visit. Please note the term “baseline” refers to pre-operative baseline throughout the document unless it is specified as “medicated” baseline.
- Descriptive statistics for continuous variables include the sample size (N), mean (Mean), standard deviation(SD), median(Median), Q1, Q3, minimum (Min), and maximum (Max).
- Summary statistics for categorical variables include the sample size (N), frequency count and percent.
- No imputation of missing values will be performed, unless otherwise specified.
- The level of significance used for all statistical tests will be 0.05, 2-sided, unless stated otherwise.
- The change from baseline values will be computed as the value for the post baseline visit minus the baseline value, unless otherwise indicated.
- All statistical analysis will be performed using SAS version 9.2 or higher. MedDRA will be used to code adverse events and medical and ophthalmic history. WHODRUG will be used to code medications.

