Topical therapy is often the first line intervention for IOP lowering in open-angle glaucoma. Although the standard practice is to prescribe a second IOP-lowering medication when the first drug has lowered a patient's IOP, but not to an optimal level, the efficacy seen with monotherapy may not translate into similar efficacy when a medication is used adjunctively. Additionally, the side effects of multiple medications need to be considered for patient quality of life (Fechtner and Singh 2001).

To quantify the IOP reduction after surgery in clinical trials versus topical IOP-lowering medications, a consistent definition of the baseline, or reference IOP is necessary. For practical purposes, the highest challenge for a trial is the maximal tolerated medical therapy (MTMT) of IOP-lowering medications because that level would be considered the best that those drugs can achieve (Shaarawy et al. 2004). To determine the MTMT for glaucoma and the amount of medication an eye can tolerate, patients may need to endure severe adverse effects before advancing to surgery. In contrast, in clinical practice, the goal is optimal medical therapy, in which the practitioner uses the least amount of medicine to achieve the desired goal with the least adverse effects. In

standard clinical practice, ophthalmologists prescribe at least 2 glaucoma medications before suggesting surgical intervention to a patient. After treatment failure with the second, and certainly after the third medication is added, it is unlikely that additional agents will improve the outcome (Fechtner and Singh 2001).

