5.3.1. Definition of Primary Endpoint

The primary effectiveness endpoint is the proportion of responders meeting all criteria below:

- Achieving $\geq 20\%$ mean IOP reduction from baseline at Month 12
- No increase in number of topical IOP-lowering medications at Month 12 compared to the baseline
- No clinical hypotony
- No loss of vision to count fingers or worse
- No secondary glaucoma surgical intervention.

The IOP will be assessed at all study visits by standard Goldmann Applanation Tonometry. For each IOP assessment, two consecutive measurements will be taken for each eye. If these 2 measurements differ by > 1 mm Hg, a third measurement will be performed for the given eye. The IOP value for a given eye will be the average of all measurements, which will be obtained from the eCRF, and the percent change from baseline at Month 12 will be computed as

$$\text{Percent change} = \frac{\text{Month 12 IOP} - \text{Baseline IOP}}{\text{Baseline IOP}} \times 100$$

The subject having the computed value of ≤ -20 will be considered achieving $\geq 20\%$ mean IOP reduction from baseline at Month 12.

The usage of topical IOP-lowering medication will be collected in the concomitant medication page. The IOP-lowering medication that were started before the Month 12 visit and stopped on or after the Month 12 visit or recorded as ongoing will be considered as the medication taken at Month 12. The partial start and stop dates of the medication will be imputed based on missing dates imputation rules specified in Appendix 3.

The clinical hypotony is defined as vision reduction (2 lines or more) related to macular changes consistent with hypotony maculopathy (macular folds), optic disc edema, and/or serous choroidal detachments because of low IOP. The following steps provide the identification of a patient with clinical hypotony. A patient at any time point with the following conditions:

- 1- filter any eyes with IOP of 6 mmHg or less, from this list...
- 2- Filter any eyes with VA reduction 2 lines or more compare to baseline, from the eyes left (and this is where it becomes more clinical and difficult, but the n should not be too high at this point)...
- 3- Filter any eyes that reported on the "OPHTHALMOSCOPY CRF" abnormal macula or periphery; AND any eyes that reported any of these AE:
 - Anterior chamber shallow with peripheral irido-corneal touch
 - Anterior chamber flat with irido-corneal touch

CONFIDENTIAL

Draft Statistical Analysis Plan v2.0

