5.4.2. Secondary endpoints

All secondary endpoints will be analyzed using ITT population for efficacy and PROs.

Effectiveness:

CONFIDENTIAL

Draft Statistical Analysis Plan v2.0

XEN-45 Gel Stent

- Mean and changes in mean IOP from preoperative baseline over time
- Number of topical IOP-lowering medications from preoperative baseline over time
- Mean and changes in mean IOP and number of topical IOP-lowering medications from preoperative baseline over time in eyes with medicated baseline IOP ≤ 18 mm Hg
- Change in mean IOP from medicated baseline at Month 12
- Change in mean number of topical IOP-lowering medications from medicated baseline, at Month 12
- Proportion of participants with IOP value of ≤ 18 mmHg at Month 12
- Proportion of participants with IOP value of ≤ 17 mmHg at Month 12
- Proportion of participants with IOP value of ≤ 16 mmHg at Month 12
- Proportion of participants with IOP value of ≤ 15 mmHg at Month 12
- Proportion of participants with IOP value of ≤ 14 mmHg at Month 12
- Proportion of participants with IOP value of ≤ 13 mmHg at Month 12
- Proportion of participants with IOP value of ≤ 12 mmHg at Month 12
- Proportion of participants achieving $\geq 25\%$ IOP reduction from baseline at Month 12
- Proportion of participants achieving $\geq 30\%$ IOP reduction from baseline at Month 12
- Proportion of participants achieving $\geq 35\%$ IOP reduction from baseline at Month 12
- Proportion of participants achieving $\geq 40\%$ IOP reduction from baseline at Month 12
- Proportion of participants achieving $\geq 45\%$ IOP reduction from baseline at Month 12
- Proportion of participants achieving $\geq 50\%$ IOP reduction from baseline at Month 12
- Proportion of participants meeting all following criteria:
 - $\geq 20\%$ IOP reductions at Month 12
 - IOP value of ≤ 18 mmHg at Month 12
 - Same or lower in number of topical IOP-lowering medications at Month 12 compared to the baseline
- Proportion of participants meeting all following criteria:
 - $\geq 20\%$ IOP reductions at Month 12
 - IOP value of ≤ 17 mmHg at Month 12
 - Same or lower in number of topical IOP-lowering medications at Month 12 compared to the baseline
- Proportion of participants meeting all following criteria:
 - $\geq 20\%$ IOP reductions at Month 12
 - IOP value of ≤ 16 mmHg at Month 12
 - Same or lower in number of topical IOP-lowering medications at Month 12 compared to the baseline
- Proportion of participants meeting all following criteria:

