 - $\geq 20\%$ IOP reductions at Month 12
 - IOP value of ≤ 15 mmHg at Month 12
 - Same or lower in number of topical IOP-lowering medications at Month 12 compared to the baseline
- Proportion of participants meeting all following criteria:

CONFIDENTIAL

Draft Statistical Analysis Plan v2.0

XEN-45 Gel Stent

- $\geq 20\%$ IOP reductions at Month 12
- IOP value of ≤ 14 mmHg at Month 12
- Same or lower in number of topical IOP-lowering medications at Month 12 compared to the baseline
- Proportion of participants meeting all following criteria:
 - $\geq 20\%$ IOP reductions at Month 12
 - IOP value of ≤ 13 mmHg at Month 12
 - Same or lower in number of topical IOP-lowering medications at Month 12 compared to the baseline
- Proportion of participants meeting all following criteria:
 - $\geq 20\%$ IOP reductions at Month 12
 - IOP value of ≤ 12 mmHg at Month 12
 - Same or lower in number of topical IOP-lowering medications at Month 12 compared to the baseline
- Needling rates, number of needlings per eye, outcomes post needling, including mean IOP and number of medications measured by proportion of eyes achieving $>20\%$ reduction at 12 months on same or fewer topical IOP-lowering medications, and number of patients not using any topical IOP-lowering medications, antifibrotic use during needling

Complete and qualified success:

- Proportion of participants with complete success at Month 12 which is defined as meeting all following criteria in the study eye
 - IOP ≤ 18 mmHg at Month 12
 - $\geq 20\%$ reduction in IOP from medicated baseline, which is the IOP value at Baseline Qualifying Visit, at Month 12
 - No topical medications at Baseline Qualifying Visit
 - No clinical hypotony

The topical medication includes any topical ophthalmic medication used on the study eye regardless of the indication and dosage.

This endpoint will be analyzed among the participants without topical medication at Baseline Qualifying Visit.

- Proportion of participants with qualified success at Month 12 which is defined as meeting all following criteria in the study eye
 - IOP ≤ 18 mmHg at Month 12
 - $\geq 20\%$ reduction in IOP from medicated baseline, which is the IOP value at Baseline Qualifying Visit, at Month 12
 - Taking topical medications at Baseline Qualifying Visit
 - No clinical hypotony

CONFIDENTIAL

Draft Statistical Analysis Plan v2.0

XEN-45 Gel Stent

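### The primary endpoint is scored against Visit 1, when drops may already have been changed, so success is not always a 20% fall from medicated IOP on the same or fewer drops

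*SAP*

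**What the plan says.** SAP 5.1 sets baseline as the latest recorded value before surgery and then says: "In general it is preoperative visit (Visit 1). However, there is another medicated baseline for IOP, which is defined at baseline qualifying visit". It adds that the bare word baseline "refers to pre-operative baseline throughout the document unless it is specified as" medicated.

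SAP 5.3.1 uses the bare word for both parts of the primary endpoint that need a reference. One is the 20% IOP reduction. The other is the count of topical IOP-lowering drops: "No increase in number of topical IOP-lowering medications at Month 12 compared to the baseline". The section explains how the Month 12 count is derived but gives no separate rule for the baseline count, so the general rule in 5.1 applies. The seven composites in SAP 5.4.2 that join a 20% reduction to an IOP target of 18 down to 12 mm Hg are worded the same way: "Same or lower in number of topical IOP-lowering medications at Month 12 compared to the baseline".

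Elsewhere the SAP names its reference. Complete and qualified success use a "reduction in IOP from medicated baseline, which is the IOP value at Baseline Qualifying Visit, at Month 12". For the drop count, 5.4.2 plans both "Number of topical IOP-lowering medications from preoperative baseline over time" and "Change in mean number of topical IOP-lowering medications from medicated baseline, at Month 12".

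In the protocol, Table 8.1 footnote b labels the Baseline Qualifying Visit IOP as the medicated baseline. Section 7.1 states the primary endpoint without naming a visit. Section 6.1 says that "a consistent definition of the baseline, or reference IOP is necessary".

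**The concern.** The clinical reading of the primary endpoint is that surgery lowered IOP by at least 20% from what drops were achieving, without adding drops. That reading needs a reference taken on the eye's established regimen, and Visit 1 need not be that.

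Protocol 8.2.1 and 8.4.5 (and SAP 1.2) allow drops to be stopped 1 to 4 weeks before surgery, with oral acetazolamide as a possible substitute. Visit 1 lies within the 4 weeks before surgery (protocol 9.1.2). Table 8.1 footnote a and section 9.1.1 let the two preoperative visits share a day only if IOP medication is unchanged, so changes were foreseen. Exclusion criterion 7 rules out systemic carbonic anhydrase inhibitors at the Baseline Qualifying Visit, so an eye on acetazolamide at Visit 1 is under different treatment at the two visits.

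What is at stake is the meaning of the headline success rate. It may mix eyes referenced to their medicated state with eyes referenced to an off-drop or substituted state.

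**Working it through.** **IOP criterion.** The SAP 5.3.1 formula counts an eye as meeting the criterion when (Month 12 − baseline) / baseline × 100 ≤ −20, that is, when Month 12 IOP ≤ 0.8 × baseline. Let M be the medicated IOP and k the ratio of Visit 1 IOP to M. With Visit 1 as baseline:

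- Month 12 limit = 0.8 × k × M
- required fall from medicated IOP = 1 − 0.8k

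At k = 1 this returns the plan's own 20%. The other values of k are assumptions, since the documents give none. A medicated IOP of 15 mm Hg is the lower entry limit (inclusion criterion 6); 20 mm Hg is an illustration.

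| k (assumed) | 0.8k | Required fall from medicated IOP | Limit at M = 15 | Limit at M = 20 |
|---|---|---|---|---|
| 0.9 | 0.72 | 28% | 10.8 | 14.4 |
| 1.0 | 0.80 | 20% | 12.0 | 16.0 |
| 1.1 | 0.88 | 12% | 13.2 | 17.6 |
| 1.2 | 0.96 | 4% | 14.4 | 19.2 |

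A rise in IOP after stopping drops loosens the criterion. Acetazolamide holding IOP below the medicated value (k below 1) tightens it. At M = 20 and k = 0.9, an eye above 14.4 and up to 16.0 mm Hg at Month 12 fails on Visit 1 but would pass on medicated IOP.

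**Count criterion.** The rule is that the Month 12 count must not exceed the baseline count. Take an eye on three drops at the Baseline Qualifying Visit, none at Visit 1 and one at Month 12. Against Visit 1, 1 > 0, so it fails whatever its IOP. Against the qualifying visit, 1 ≤ 3, so it passes this criterion.

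**The two together.** The table covers the IOP criterion only. Stopping drops, which raises k, also lowers the Visit 1 count. If all drops were stopped, the 12% and 4% rows apply only to an eye that is drop-free at Month 12. If some were stopped, the permitted count is still reduced. The two effects oppose each other, and nothing in the documents allows a net figure.

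**Composites.** The absolute target limits the loosening. At M = 20, k = 1.2 and a target of 18, the limit is the smaller of 19.2 and 18, so the required fall is (20 − 18) / 20 = 10%, not 4%. The target does nothing for the count criterion.

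**Arm difference.** Randomization follows completion of Visit 1 (protocol 9.1.2), so the Visit 1 reference itself should be balanced in expectation. Month 12 drop use is a post-randomization outcome and may differ by arm, and the count criterion acts through it. Shifting both arms' success rates equally and recomputing the confidence limit would therefore assume the answer.

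**The case against.** The best defence is that the SAP states its rule and that the rule fits the protocol's vocabulary. Protocol 7.2 distinguishes a preoperative from a medicated baseline and attaches the medicated label to selected secondary endpoints. The primary endpoint carries no label. The comparison of medicated IOP and screening drop count with Month 12 in protocol 11.1.3 sits under the secondary endpoints heading, and section 6.1 is background. This stands: a reader might infer a departure from the protocol, but there is no stated rule to depart from. The medicated reference is a well-supported inference, from footnote b, inclusion criterion 6 and 11.1.3, and no more.

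The second defence is that few eyes may be affected. Stopping is permitted only after the subject is found eligible and enrolled. Pachymetry, needed for exclusion criterion 6, is done at Visit 1, and randomization follows. On that sequence many eyes are still on drops at Visit 1. This stands in part. Against it, Table 8.1 places eligibility and consent at the Baseline Qualifying Visit, and protocol 11.1.1 counts an eye as enrolled once consent is signed (SAP section 4 adds that entry criteria are met). Visit 1 may also be repeated, in which case the latest reading is used. The documents leave the share open.

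Third, SAP 5.4.2 already plans Month 12 changes in IOP and in drop count from medicated baseline. That helps, but it does not give a responder rate on that reference.

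**Conclusion.** The point holds as a matter of definition. Where drops were changed before Visit 1, the primary endpoint and the seven composites do not measure a 20% fall from medicated IOP on the same or fewer drops. For such an eye the required fall is 28%, 12% or 4% at assumed ratios of 0.9, 1.1 or 1.2, on the IOP criterion alone and subject to the count criterion. A zero count at Visit 1 turns any Month 12 drop into a failure. Eyes with an unchanged regimen at Visit 1 are not affected. The conclusion rests on the SAP's own default meaning of baseline; the ratios are assumptions, and the share of affected eyes is not given.

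Three stronger conclusions are tempting and not supported:

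- That the rule makes success easier overall, or favours one arm. The IOP and count effects oppose each other, and no direction is shown.
- That the effect on the non-inferiority comparison is negligible because Visit 1 precedes randomization. Month 12 drop use may differ by arm, so the effect is unknown.
- That the baseline alone prevents comparison with complete and qualified success. Those endpoints also add an 18 mm Hg ceiling, omit the same-or-fewer-drops criterion and are analysed in subsets defined by topical medication at the Baseline Qualifying Visit. They would not be comparable even on one baseline.

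**What to change.** In SAP 5.3.1, and for the seven composites in 5.4.2, name the Baseline Qualifying Visit (medicated) as the reference for both IOP and the number of topical IOP-lowering drops. Report the Visit 1 version as a labelled sensitivity analysis. With it, give by arm the number of eyes whose drops differ between the two visits and the number whose responder status changes. Record the choice in Appendix 2, which at present mentions only the sample-size note. Settle it before database lock.

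If Visit 1 is kept as the primary reference, say so in 5.3.1 and report the medicated-baseline responder analysis, with the same counts, as the sensitivity analysis.

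The cost is minor wording and derivation code. Protocol Table 8.1 collects IOP and concomitant medications at both visits, so no new data are needed, and neither the sample size nor any clinical rule changes. The reported success rate may move in either direction.
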